14.3.5 HDA and long-term responders

Responder rates will be analyzed in HDA patients versus the responder rate in non-HDA patients from the Cohort B population and summarized descriptively for the FAS population.

14.3.6 Genetic variations

Optional blood samples for pharmacogenetics testing will be collected at Study Visit 1. The current plan for PGx is to identify ~20 Single Nucleotide Polymorphism (SNPs) that will be analyzed and validated prior to using in the PGx analysis. Identification of SNP is the responsibility of Clinical Biomarkers and Companion Diagnostics group (CBD) and will be documented in separate document (Appendix 17.4). The PGx analysis will be done approximately 2 years after study completion. The result may be presented on a separate CSR as an addendum to the CSR. The main approach will be to analyze SNP or combination of SNPs subgroup variables with 2-3 categories on primary and secondary endpoints. The rules about analyzing data with small cells or zero cells will be similar to other subgroup analysis. The subgroup analysis for a variable will not be done if we have less than 25% of participant by at least 1 subgroup category in that variable.

Genetic variations will be analyzed descriptively for the primary and secondary endpoints on PGx population based on cohort A. In addition, association of genetic variations with patients experiencing long- term response will be analyzed. Correlations with clinical/imaging endpoints and other data will be explored.

15 Safety Analyses

The subsections in this section include specifications for summarizing safety assessments: adverse events, laboratory tests and vital signs.

15.1 Adverse Events

15.1.1 All Adverse Events

AEs include all AEs which start on or after the CLASSIC ICF signature and will be displayed in listings. All CRF data will be included in the listings, including start and end date, seriousness, severity, Adverse Drug reaction (ADR) will be listed.

All AEs will be summarized using the latest version of MedDRA preferred term (PT) and

MedDRA primary system organ class (SOC) body term as Body System category.

No imputation will be done on listings.

All listings will be grouped by treatment groups for cohort A, FAS analysis set.

15.1.2 Adverse Events Leading to Discontinuation of Study Treatment

Not Applicable

15.2 Deaths, Other Serious Adverse Events, and Other Significant Adverse Events

15.2.1 Deaths

AEs leading to death will be reported in a listing.

15.2.2 Serious Adverse Events

Serious AEs will be reported in a listing.

15.2.3 Other Significant Adverse Events

Three AEs of special interest (AESIs) will be listed:

- Severe (\geq Grade 3) lymphopenia
- Infections/ opportunistic infections
- Malignancies

AESI will be identified using the “adverse drug reactions related to cladribine or placebo since the end of parent studies details” eCRF page. Only AESI collected via eCRF will be reported in a listing.

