6.9 Management of Adverse Events of Interest

Adverse events of special interest (AESIs) for this study as defined in the SmPC should be considered as a medically significant AE and reported to the Sponsor using a Serious Adverse Event (SAE) Report Form with all related information.

Three main categories of AEs were defined as AESI:

- Severe (\geq Grade 3) lymphopenia: Lymphopenia is an expected event based on the mechanism of action of cladribine, an adenosine deaminase-resistant analog of deoxyadenosine, that after conversion to its active triphosphate form (2-Cd-ATP), decreases peripheral lymphocyte counts; grading should be performed according Common Terminology Criteria for Adverse Events where Grade 3 is defined as $< 500/\text{mm}^3$ - $200/\text{mm}^3$.
- Infections: Defects in cell-mediated immunity and immunosuppressive conditions may predispose patients to infectious diseases.
- Malignancies: Immunodeficiency could lead to an increased risk for the development of malignancies; however, this is generally seen where immunosuppression is profound and long-lasting. Malignancy cases have been reported in MS patients treated with other DMDs. In view of these considerations the potential risk of malignancy for Cladribine Tablets has been thoroughly evaluated.

7 Discontinuation of Study Intervention and Participant Discontinuation/Withdrawal

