It is important that each AE report include a description of the event, its duration (onset and resolution dates and also onset and resolution times, when it is important to assess the time of AE onset relative to the recorded study intervention administration time), its severity, its causal relationship with the study intervention, any other potential causal factors, any treatment given or other action taken, including dose modification or discontinuation of the study intervention, and its outcome. In addition, serious cases should be identified, and the appropriate seriousness criteria documented.

Specific guidance is in the CRF Completion and Monitoring Conventions provided by the Sponsor.

Reporting Serious Adverse Events and Adverse Events of Special Interest

Serious Adverse Events

In the event of any new SAE occurring during the reporting period, the Investigator must immediately (within a maximum of 24 HOURS after becoming aware of the event) inform the Sponsor or its designee using the electronic SAE report form in the electronic data capture (EDC) system. Any ADRs (assessed as related to cladribine by the Investigator after the End of Trial Visit in the parent study CLARITY/ORACLE/CLARITY-EXT) must be recorded in the eCRF as well. If the ADR information is captured in the subject's medical chart already at the time of enrolment then the event is not considered to be of new awareness and it is expected to be reported in the Medical History page (e.g. awareness date prior to ICF date). If the ADR is reported by the patient at the time of enrolment or after that then the event is considered of new awareness, and it is expected to be reported in the ADR page (e.g. awareness date is after ICF date). Reporting of SAEs using a paper report form is required as a back-up method only for an EDC system failure. Names, addresses, and telephone and fax numbers will be included on the paper form. All information from the paper form must be transcribed into the electronic form as soon as the system becomes available.

In exceptional circumstances, an SAE (or follow-up information) may be reported by telephone; in these cases, an electronic SAE report form must be completed immediately thereafter.

Relevant pages from the CRF may be provided in parallel (e.g., medical history, concomitant drugs). Additional documents may be provided by the Investigator, if available (e.g., laboratory results, hospital report, autopsy report).

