The Investigator must respond to any request for follow-up information (e.g., additional information, outcome, final evaluation, other records where needed) or to any question the Sponsor/designee may have on the AE within the same timelines as those noted above for initial reports. This is necessary to ensure prompt assessment of the event by the Sponsor

or designee and (as applicable) to allow the Sponsor to meet strict regulatory timelines associated with expedited safety reporting obligations.

Requests for follow-up will usually be made via the study monitor, although in exceptional circumstances the drug safety department may contact the Investigator directly to obtain further information or to discuss the event.

Adverse Events of Special Interest

In the event of a non-serious AESI, the Investigator will notify the Sponsor/designee by completing the electronic AESI Report Form in the EDC system. Serious AESIs must be reported in an expedited manner as SAEs, as outlined above. Reporting of non-serious AESIs using a paper report form is required as a back-up method only for an EDC system failure. Names, addresses, and telephone and fax numbers will be included on the paper report form. All information from the paper form must be transcribed into the electronic form as soon as the system becomes available.

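### The AESI listing is built from the adverse drug reaction page alone, so AESIs that the protocol records elsewhere, or that are judged unrelated, would be left out of it

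*SAP*

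**What the plan says.** SAP 15.2.3 names three AESI groups: severe lymphopenia (Grade 3 or higher), infections and malignancies. It gives one source for them: "AESI will be identified using the “adverse drug reactions related to cladribine or placebo since the end of parent studies details” eCRF page". The next sentence adds: "Only AESI collected via eCRF will be reported in a listing". The output is Listing 16.2.7.4, for Cohort A.

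The protocol describes several places where such an event may be recorded:

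- **Appendix 3, reaction already in the chart at enrolment:** "the event is not considered to be of new awareness and it is expected to be reported in the Medical History page".
- **Appendix 3, reaction reported by the patient at or after enrolment:** "the event is considered of new awareness, and it is expected to be reported in the ADR page".
- **Appendix 3, AESIs:** "In the event of a non-serious AESI, the Investigator will notify the Sponsor/designee by completing the electronic AESI Report Form in the EDC system". An AESI that is serious is handled as an SAE.
- **Section 8.2:** clinically significant abnormalities before consent belong in the medical or disease history; those arising or worsening after consent belong in the AE section.
- **Section 6.9:** an AESI "should be considered as a medically significant AE and reported to the Sponsor using a Serious Adverse Event (SAE) Report Form", with no distinction between serious and non-serious.
- **Section 8.3.1:** a reaction after the parent End of Trial Visit is recorded as an ADR when the investigator judges it related to Cladribine Tablets. The AESI groups in Section 6.9 have no such condition.

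**The concern.** The listing's title and its source do not match. A reader who opens Listing 16.2.7.4 to see how many malignancies, infections or severe lymphopenias were recorded will take it as complete. The source rule makes it a list of one kind of AESI: those judged related and entered on one page. A malignancy that the investigator considers unrelated is an AESI under protocol 6.9, yet it has no place on the ADR page. The same holds for an infection entered only in the AE section.

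What is at stake is the completeness of one safety output and the impression that a short listing would give. No efficacy endpoint is affected.

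**Working it through.** No arithmetic applies, because the documents give no AESI count. The check traces each protocol route to the single source in SAP 15.2.3 and to the other planned outputs.

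| Event | Recorded where (protocol) | Read for Listing 16.2.7.4? | Other output (SAP 17.1) |
|---|---|---|---|
| Related reaction after the parent study, reported by the patient at or after enrolment | ADR page (Appendix 3) | Yes | – |
| Related reaction already in the chart at enrolment | Medical History page (Appendix 3) | No | Medical History tables and Listing 16.2.3.1 |
| Pre-consent infection, malignancy or lymphopenia not judged related | Medical or disease history (8.2) | No | Same, if on the Medical History page |
| Non-serious AESI after consent | AE section (8.2) and AESI Report Form (Appendix 3) | Only if judged related and also on the ADR page | Listing 16.2.7.1 |
| Serious AESI after consent | AE section (8.2) and SAE form (Appendix 3) | Only if judged related and also on the ADR page | Listings 16.2.7.1 and 16.2.7.2, and 16.2.7.3 if fatal |

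Four things follow.

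1. **Where the restriction comes from.** The sentence about eCRF collection would not by itself exclude the AE page or the electronic AESI form. The sentence before it, which names the ADR page, creates the gap.

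2. **A concrete case.** Appendix 3 makes any positive COVID-19 test an AE, and infections are an AESI group. Unless the investigator judges the infection related to cladribine, it sits in the AE section and is absent from Listing 16.2.7.4.

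3. **Whether another output repairs it.** The AE outputs start at CLASSIC consent (SAP 15.1.1). The medical history outputs (SAP 11.2) are not split into conditions before and after the parent study. Neither these nor the SAE listing flags AESIs, and no planned output brings the three groups together across pages.

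4. **Size.** Let *s* be the share of all recorded AESIs that reach the ADR page. The share omitted is 1 − *s*. The documents give no *s* and nothing from which to derive it, so the omitted share could lie anywhere from 0% to 100%.

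**The case against.** The strongest reply is that the ADR page may be a wider source than Appendix 3 suggests. The Schedule of Activities (Section 1.3) places cladribine-related reactions under retrospective chart review at Study Visit 1. The page's name covers the whole period since the parent studies, and Section 8.3.1 requires every related reaction after the parent End of Trial Visit to be recorded in the eCRF. If sites followed those passages, chart-documented reactions could be on the ADR page after all. This stands as a real ambiguity in the protocol. It would narrow the gap but not close it: AESIs judged unrelated, and those entered only on the AE, SAE or AESI forms, would still be missed.

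Three further points stand:

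- Protocol 8.2 states that the study has no specific safety endpoints, so this listing is not a central product of the study.
- The events are not lost. AEs and medical history are summarised by preferred term and system organ class, so infections and malignancies can be found there.
- A term search will not always establish Grade 3 or higher. Section 6.9 grades lymphopenia by CTCAE, but Appendix 3 grades AEs as mild, moderate or severe, and Section 8.2.4 provides for no safety laboratory tests.

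The conflict between Section 6.9 and Appendix 3 over forms concerns reporting to the sponsor. It is a separate matter from how the SAP builds its listing.

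**Conclusion.** The point holds as a wrong source rule in SAP 15.2.3. If the listing is programmed as written, it omits by design any AESI that is not on the ADR page, including those judged unrelated. How many that would be cannot be determined. The conclusion assumes that sites follow Appendix 3 and Section 8.2 when choosing a page.

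A reader might go further and infer that most AESIs would be missing. Study visits fall around 10 years after initial treatment (protocol Section 9), while prospective participation lasts at most about 6 months. That is 0.5/10 = 5% of the time, or 0.5/8 = 6.25% if 8 years is assumed. The documents do not support the inference. Appendix 3 divides reactions by when the site became aware of them, not by when they began, so a reaction from years ago reaches the ADR page if the patient first mentions it at enrolment. The ADR page and the Medical History page therefore cover the same years, and a ratio of follow-up times says nothing about the share of events lost. Nor do the documents show that the listing would be nearly empty.

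**What to change.** Replace the source rule in SAP 15.2.3. Identify AESIs by a prespecified MedDRA search for lymphopenia, infections and malignancies across the ADR, AE, SAE/AESI and Medical History pages. Limit Medical History to entries dated after the parent End of Trial Visit. For each event show the source page, onset date, relatedness and exposure group (exposed or never exposed to cladribine, as in SAP 8.2.1). Where Grade 3 or higher cannot be established, list the lymphopenia with its grade shown as unknown.

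SAP 9.2 already provides MedDRA coding for AEs and medical history. The team should confirm that ADR-page and AESI-form entries are coded too, and that Medical History entries carry a usable date.

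Separately, two sets of protocol passages must be reconciled: Section 6.9 with Appendix 3 on the AESI reporting form, and Sections 1.3 and 8.3.1 with Appendix 3 on where chart-documented reactions are recorded.

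The cost is a paragraph of SAP text, a term list and a small amount of extra programming. No new data collection is proposed. The downside is that some lymphopenia entries will be of unknown grade.

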15.3 Clinical Laboratory Evaluation

Pregnancy test collected on the eCRF will be listed in dedicated listings.

15.4 Vital Signs

Vital sign summaries will include all vital sign assessments collected at Study visit 1 in the CRF (systolic and diastolic blood pressure (mmHg), pulse rate (BPM) and body temperature (C)]. All vital sign assessments will be listed only.

17.1 Table: List of outputs for the interim and final analyses

Outputs	Title	Interim Analysis	Type (Unique, Repeated)
15.1 Demographic and Baseline Data			
15.1.1 Subject Disposition			
Table 15.1.1.1	Subject Disposition – FAS analysis set	Y	U
Table 15.1.1.2	Analysis Sets	Y	U
15.1.2 Important Protocol Deviations			
Table 15.1.2.1	Important Protocol Deviations- FAS analysis set		U
15.1.4 Demographic and Baseline Characteristics			
Table 15.1.4.1	Demographics and baseline characteristics- Cohort A- FAS analysis set	Y	U
Table 15.1.4.2	Demographics and baseline characteristics- Cohort B- FAS analysis set	Y	
Table 15.1.4.3	Demographics and baseline characteristics- Cohort C- FAS analysis set	Y	
Table 15.1.4.4	Demographics and baseline characteristics- Cohort D- FAS analysis set	Y	
Table 15.1.4.5	Distribution by Region and Country - FAS analysis set		U
15.1.5: Medical history			
Table 15.1.5.1	Medical History- Cohort A- FAS analysis set	Y	U
Table 15.1.5.2	Medical History- Cohort B- FAS analysis set		
Table 15.1.5.3	Medical History- Cohort C- FAS analysis set		
Table 15.1.5.4	Medical History- Cohort D- FAS analysis set		
15.1.7: Previous and concomitant Medications, Procedures, Follow-up			
Table 15.1.7.1	Prior and Concomitant Medications in CLASSIC - Cohort A- FAS analysis set		U

Table 15.1.7.2	Disease Modifying Drug for MS subsequent to IMP treatment in Parent study by Type/ATC - FAS analysis set	Y	U
Table 15.1.7.3	Disease Modifying Drug for MS subsequent to IMP treatment in Parent Study by Type/ATC - Cohort A- FAS analysis set	Y	
Table 15.1.7.4	Disease Modifying Drug for MS subsequent to IMP treatment in Parent Study by Type/ATC - Cohort B- FAS analysis set	Y	
Table 15.1.7.5	Disease Modifying Drug for MS subsequent to IMP treatment in Parent Study by Type/ATC - Cohort C - FAS analysis set	Y	
Table 15.1.7.6	Disease Modifying Drug for MS subsequent to IMP treatment in Parent Study by Type/ATC - Cohort D - FAS analysis set	Y	
Table 15.1.7.7	Pattern of Disease Modifying Drug Types for MS subsequent to Cladribine treatment after First Dose of IMP - Cohort A - FAS analysis set	Y	U
Table 15.1.7.8	Pattern of Disease Modifying Drug Types for MS subsequent to Cladribine treatment after First Dose of IMP - Cohort B - FAS analysis set	Y	
Table 15.1.7.9	Pattern of Disease Modifying Drug Types for MS subsequent to Cladribine treatment after First Dose of IMP - Cohort C - FAS analysis set	Y	
Table 15.1.7.10	Pattern of Disease Modifying Drug Types for MS subsequent to Cladribine treatment after First Dose of IMP - Cohort D - FAS analysis set	Y	
Table 15.1.7.11	Pattern of Disease Modifying Drug Types for MS subsequent to Cladribine treatment after Last Dose of IMP - Cohort A - FAS analysis set	Y	
Table 15.1.7.12	Pattern of Disease Modifying Drug Types for MS subsequent to Cladribine treatment after Last Dose of IMP - Cohort B - FAS analysis set	Y	
Table 15.1.7.13	Pattern of Disease Modifying Drug Types for MS subsequent to Cladribine treatment after Last Dose of IMP - Cohort C - FAS analysis set	Y	
Table 15.1.7.14	Pattern of Disease Modifying Drug Types for MS subsequent to Cladribine treatment after Last Dose of IMP - Cohort D - FAS analysis set	Y	
Table 15.1.7.15	Disease Modifying Drug for MS Subsequent to Cladribine Treatment by Type/ATC/Medication Name - FAS Analysis Set	Y	
15.2: Efficacy Data			
15.2.1: Primary Endpoint			

Table 15.2.1.1.1	Proportion of patients using a wheelchair (EDSS>=7) the majority of the time in the 3 months prior to Study Visit 1 or bedridden- Cohort A- FAS analysis set	Y	U
Table 15.2.1.1.2	Proportion of patients using a wheelchair (EDSS>=7) the majority of the time in the 3 months prior to Study Visit 1 or bedridden – Cohort A- FAS analysis set- Subset Long-term Responder		
Table 15.2.1.1.3	Proportion of patients using a wheelchair (EDSS>=7) the majority of the time in the 3 months prior to Study Visit 1 or bedridden – Cohort A- FAS analysis set- subset Types of Subsequent DMDs		
Table 15.2.1.1.4	Proportion of patients using a wheelchair (EDSS>=7) the majority of the time in the 3 months prior to Study Visit 1 or bedridden – Cohort A- FAS analysis set- Subset Long-term Responder (Sensitivity Def B)		
Table 15.2.1.1.5	Proportion of patients using a wheelchair (EDSS>=7) the majority of the time in the 3 months prior to Study Visit 1 or bedridden – Cohort A- FAS analysis set- Subset Long-term Responder (Sensitivity Def C)		
Table 15.2.1.2.1	Proportion of patients using a wheelchair (EDSS>=7) the majority of the time in the 3 months prior to Study Visit 1 or bedridden – Cohort B- FAS analysis set		
Table 15.2.1.2.2	Proportion of patients using a wheelchair (EDSS>=7) the majority of the time in the 3 months prior to Study Visit 1 or bedridden – Cohort B- FAS analysis set- Subgroup Treatment course		
Table 15.2.1.2.3	Proportion of patients using a wheelchair (EDSS>=7) the majority of the time in the 3 months prior to Study Visit 1 or bedridden – Cohort B- FAS analysis set- Subset Long-term Responder		
Table 15.2.1.2.4	Proportion of patients using a wheelchair (EDSS>=7) the majority of the time in the 3 months prior to Study Visit 1 or bedridden – Cohort B- FAS analysis set- subset Types of Subsequent DMDs		
Table 15.2.1.2.5	Proportion of patients using a wheelchair (EDSS>=7) the majority of the time in the 3 months prior to Study Visit 1 or bedridden – Cohort B- FAS analysis set- Subgroup Prior Use of DMD		
Table 15.2.1.2.6	Proportion of patients using a wheelchair (EDSS>=7) the majority of the time in the 3 months prior to Study Visit 1 or bedridden – Cohort B- FAS analysis set- Subgroup HDA		
Table 15.2.1.2.7	Proportion of patients using a wheelchair (EDSS>=7) the majority of the time in the 3 months prior to Study Visit 1 or bedridden – Cohort B- FAS analysis set- Subset Long-term Responder (Sensitivity Def B)		
Table 15.2.1.2.8	Proportion of patients using a wheelchair (EDSS>=7) the majority of the time in the 3 months prior to Study Visit 1 or bedridden – Cohort B- FAS analysis set- Subset Long-term Responder		

	(Sensitivity Def C)		
Table 15.2.1.3.1	Proportion of patients using a wheelchair (EDSS>=7) the majority of the time in the 3 months prior to Study Visit 1 or bedridden – Cohort C- FAS analysis set		
Table 15.2.1.3.2	Proportion of patients using a wheelchair (EDSS>=7) the majority of the time in the 3 months prior to Study Visit 1 or bedridden – Cohort C- FAS analysis set- Subset Long-term Responder		
Table 15.2.1.3.3	Proportion of patients using a wheelchair (EDSS>=7) the majority of the time in the 3 months prior to Study Visit 1 or bedridden – Cohort C- FAS analysis set- Subset Types of Subsequent DMDs		
Table 15.2.1.3.4	Proportion of patients using a wheelchair (EDSS>=7) the majority of the time in the 3 months prior to Study Visit 1 or bedridden – Cohort C- FAS analysis set- Subset Long-term Responder (Sensitivity Def B)		
Table 15.2.1.3.5	Proportion of patients using a wheelchair (EDSS>=7) the majority of the time in the 3 months prior to Study Visit 1 or bedridden – Cohort C- FAS analysis set- Subset Long-term Responder (Sensitivity Def C)		
Table 15.2.1.4.1	Proportion of patients using a wheelchair (EDSS>=7) the majority of the time in the 3 months prior to Study Visit 1 or bedridden – Cohort D- FAS analysis set		
Table 15.2.1.4.2	Proportion of patients using a wheelchair (EDSS>=7) the majority of the time in the 3 months prior to Study Visit 1 or bedridden – Cohort D- FAS analysis set- Subset Long-term Responder		
Table 15.2.1.4.3	Proportion of patients using a wheelchair (EDSS>=7) the majority of the time in the 3 months prior to Study Visit 1 or bedridden – Cohort D- FAS analysis set- Subset Types of Subsequent DMDs		
Table 15.2.1.4.4	Proportion of patients using a wheelchair (EDSS>=7) the majority of the time in the 3 months prior to Study Visit 1 or bedridden – Cohort D- FAS analysis set- Subset Long-term Responder (Sensitivity Def B)		
Table 15.2.1.4.5	Proportion of patients using a wheelchair (EDSS>=7) the majority of the time in the 3 months prior to Study Visit 1 or bedridden – Cohort D- FAS analysis set- Subset Long-term Responder (Sensitivity Def C)		
Figure 15.2.1.1.1	Forest Plot of Proportion of patients using a wheelchair (EDSS>=7) the majority of the time in the 3 months prior to Study Visit 1 or bedridden- Cohort A- FAS analysis set		
15.2.2: Secondary Endpoint 1			

Table 15.2.2.1.1	Proportion of patients with EDSS of 6.0 or higher since last dose of IMP – Cohort A- FAS analysis set	Y	U
Table 15.2.2.1.2	Proportion of patients with EDSS of 6.0 or higher since last dose of IMP– Cohort A- FAS analysis set- Subset Long-term Responder		
Table 15.2.2.1.3	Proportion of patients with EDSS of 6.0 or higher since last dose of IMP– Cohort A- FAS analysis set- Subset Types of Subsequent DMDs		
Table 15.2.2.1.4	Proportion of patients with EDSS of 6.0 or higher since last dose of IMP– Cohort A- FAS analysis set- Subset Long-term Responder (Sensitivity Def B)		
Table 15.2.2.1.5	Proportion of patients with EDSS of 6.0 or higher since last dose of IMP– Cohort A- FAS analysis set- Subset Long-term Responder (Sensitivity Def C)		
Table 15.2.2.2.1	Proportion of patients with EDSS of 6.0 or higher since last dose of IMP – Cohort B- FAS analysis set		
Table 15.2.2.2.2	Proportion of patients with EDSS of 6.0 or higher since last dose of IMP – Cohort B- FAS analysis set- Subgroup Treatment Course		
Table 15.2.2.2.3	Proportion of patients with EDSS of 6.0 or higher since last dose of IMP – Cohort B- FAS analysis set- Subset Long-term Responder		
Table 15.2.2.2.4	Proportion of patients with EDSS of 6.0 or higher since last dose of IMP – Cohort B- FAS analysis set- Subset Types of Subsequent DMDs		
Table 15.2.2.2.5	Proportion of patients with EDSS of 6.0 or higher since last dose of IMP – Cohort B- FAS analysis set- Subgroup Prior Use of DMDs		
Table 15.2.2.2.6	Proportion of patients with EDSS of 6.0 or higher since last dose of IMP – Cohort B- FAS analysis set- Subgroup HDA		
Table 15.2.2.2.7	Proportion of patients with EDSS of 6.0 or higher since last dose of IMP– Cohort B- FAS analysis set- Subset Long-term Responder (Sensitivity Def B)		
Table 15.2.2.2.8	Proportion of patients with EDSS of 6.0 or higher since last dose of IMP– Cohort B- FAS analysis set- Subset Long-term Responder (Sensitivity Def C)		
Table 15.2.2.3.1	Proportion of patients with EDSS of 6.0 or higher since last dose of IMP –Cohort C- FAS analysis set		
Table 15.2.2.3.2	Proportion of patients with EDSS of 6.0 or higher since last dose of IMP –Cohort C- FAS analysis set- Subset Long-term Responder		

Table 15.2.2.3.3	Proportion of patients with EDSS of 6.0 or higher since last dose of IMP –Cohort C- FAS analysis set- Subset Types of Subsequent DMDs		
Table 15.2.2.3.4	Proportion of patients with EDSS of 6.0 or higher since last dose of IMP– Cohort C- FAS analysis set- Subset Long-term Responder (Sensitivity Def B)		
Table 15.2.2.3.5	Proportion of patients with EDSS of 6.0 or higher since last dose of IMP– Cohort C- FAS analysis set- Subset Long-term Responder (Sensitivity Def C)		
Table 15.2.2.4.1	Proportion of patients with EDSS of 6.0 or higher since last dose of IMP –Cohort D- FAS analysis set		
Table 15.2.2.4.2	Proportion of patients with EDSS of 6.0 or higher since last dose of IMP –Cohort D- FAS analysis set- Subset Long-term Responders		
Table 15.2.2.4.3	Proportion of patients with EDSS of 6.0 or higher since last dose of IMP –Cohort D- FAS analysis set- Subset Types of Subsequent DMDs		
Table 15.2.2.4.4	Proportion of patients with EDSS of 6.0 or higher since last dose of IMP– Cohort D- FAS analysis set- Subset Long-term Responder (Sensitivity Def B)		
Table 15.2.2.4.5	Proportion of patients with EDSS of 6.0 or higher since last dose of IMP– Cohort D- FAS analysis set- Subset Long-term Responder (Sensitivity Def C)		
Table 15.2.2.5.1	Worse EDSS since last dose of IMP – Cohort A – FAS analysis set	Y	U
15.2.3: Secondary Endpoint 2			
Table 15.2.3.1.1	Clinical characteristics at Study Visit 1 of long-term responders vs non-responders –Cohort A -FAS analysis set	Y	U
Table 15.2.3.1.2	Clinical characteristics at Study Visit 1 of long-term responders vs non-responders –Cohort A -FAS analysis set (Sensitivity Def B)		
Table 15.2.3.1.3	Clinical characteristics at Study Visit 1 of long-term responders vs non-responders –Cohort A -FAS analysis set (Sensitivity Def C)		
Table 15.2.3.2.1	Clinical characteristics at Study Visit 1 of long-term responders vs non-responders – Cohort B -FAS analysis set		
Table 15.2.3.2.2	Clinical characteristics at Study Visit 1 of long-term responders vs non-responders –Cohort B -FAS analysis set (Sensitivity Def B)		
Table 15.2.3.2.3	Clinical characteristics at Study Visit 1 of long-term responders vs non-responders –Cohort B -FAS analysis set (Sensitivity Def C)		

Table 15.2.3.3.1	Clinical characteristics at Study Visit 1 of long-term responders vs non-responders – Cohort C -FAS analysis set		
Table 15.2.3.3.2	Clinical characteristics at Study Visit 1 of long-term responders vs non-responders –Cohort C -FAS analysis set (Sensitivity Def B)		
Table 15.2.3.3.3	Clinical characteristics at Study Visit 1 of long-term responders vs non-responders –Cohort C -FAS analysis set (Sensitivity Def C)		
Table 15.2.3.4.1	Clinical characteristics at Study Visit 1 of long-term responders vs non-responders – Cohort D -FAS analysis set		
Table 15.2.3.4.2	Clinical characteristics at Study Visit 1 of long-term responders vs non-responders –Cohort D -FAS analysis set (Sensitivity Def B)		
Table 15.2.3.4.3	Clinical characteristics at Study Visit 1 of long-term responders vs non-responders –Cohort D -FAS analysis set (Sensitivity Def C)		
15.2.4: Secondary Endpoint 3			
Table 15.2.4.1.1	MRI characteristics at Study Visit 2 of long-term responders vs non-responders – Cohort A – MRISS analysis set		U
Table 15.2.4.1.2	MRI characteristics at Study Visit 2 of long-term responders vs non-responders – Cohort A – MRISS analysis set (Sensitivity Def B)		
Table 15.2.4.1.3	MRI characteristics at Study Visit 2 of long-term responders vs non-responders – Cohort A – MRISS analysis set (Sensitivity Def C)		
Table 15.2.4.2.1	MRI characteristics at Study Visit 2 of long-term responders vs non-responders – Cohort B – MRISS analysis set		
Table 15.2.4.2.2	MRI characteristics at Study Visit 2 of long-term responders vs non-responders – Cohort B – MRISS analysis set (Sensitivity Def B)		
Table 15.2.4.2.3	MRI characteristics at Study Visit 2 of long-term responders vs non-responders – Cohort B – MRISS analysis set (Sensitivity Def C)		
Table 15.2.4.3.1	MRI characteristics at Study Visit 2 of long-term responders vs non-responders – Cohort C- MRISS analysis set		
Table 15.2.4.3.2	MRI characteristics at Study Visit 2 of long-term responders vs non-responders – Cohort C – MRISS analysis set (Sensitivity Def B)		
Table 15.2.4.3.3	MRI characteristics at Study Visit 2 of long-term responders vs non-responders – Cohort C – MRISS analysis set (Sensitivity Def C)		
Table 15.2.4.4.1	MRI characteristics at Study Visit 2 of long-term responders vs non-responders – Cohort D- MRISS analysis set		
Table 15.2.4.4.2	MRI characteristics at Study Visit 2 of long-term responders vs non-responders – Cohort D – MRISS analysis set (Sensitivity Def B)		
Table 15.2.4.4.3	MRI characteristics at Study Visit 2 of long-term responders vs non-responders – Cohort D – MRISS analysis set (Sensitivity Def C)		

15.2.5: Tertiary Endpoint 1			
Table 15.2.5.1	Real-world treatment patterns in study participants – Cohort A- FAS analysis set		U
15.2.6: Tertiary Endpoint 2			
Table 15.2.6.1	Durability of clinical outcome– Cohort A – FAS analysis set		U
Table 15.2.6.2	Kaplan Meier- Time to first ambulatory device/wheelchair - Cohort A -FAS analysis set	Y	U
Figure 15.2.6.1	Kaplan Meier- Time to first ambulatory device/wheelchair by Exposed/Never Exposed Group - Cohort A -FAS analysis set	Y	U
Figure 15.2.6.2	Kaplan Meier - Time to First Ambulatory Device/Wheelchair - Cohort A - FAS Analysis Set	Y	
15.2.7: Tertiary Endpoint 3			
Table 15.2.7.1	Change in Quality of life outcomes – Cohort A- FAS analysis set	Y	U
Table 15.2.7.2	Change in Cognition outcomes (BVMT-R score)– Cohort D- FAS analysis set		U
Table 15.2.7.3	Change in Cognition outcomes (SDMT score) – Cohort D- FAS analysis set		U
15.2.8: Tertiary Endpoint 4			
Table 15.2.8.1	Change in MRI assessment from Baseline to Study Visit 2– Cohort A -MIRISS analysis set		U
15.2.9: Tertiary Endpoint 5			
Table 15.2.9.1	Responder rate by HDA/Non-HDA patients – Cohort B-FAS analysis set		U
15.2.10: Additional analysis			
Table 15.2.10.1	Additional analysis: Comparison between baseline characteristics from Non-CLASSIC/CLASSIC patients- WPS analysis set		U
15.2.11: PGX Analysis (tables will be repeated for each SNP or combination of SNPs.)			
Table 15.2.11.1.1	Proportion of patients using a wheelchair (EDSS>=7) the majority of the time in the 3 months prior to Study Visit 1 or bedridden – Cohort A – Subgroup with Presence of SNP1 gene - PGX Population		
Table 15.2.11.2.1	Proportion of patients with EDSS of 6.0 or higher since last dose of IMP – Cohort A – Subgroup with Presence of SNP1 gene - PGX Population		

Table 15.2.11.3.1	Clinical characteristics at Study Visit 1 of long-term responders vs Non-Responders – Cohort A– Subgroup with Presence of SNP1 gene - PGX Population		
Table 15.2.11.4.1	MRI characteristics at Study Visit 2 of long-term responders vs Non-Responders – Cohort A – Subgroup with Presence of SNP1 gene – PGX/MRISS Population		
